Shoot habituation was done to make family members accustomed to the creative team and equipment (lights and cameras) inside their households. This was done such that the final visuals were as close to real life interactions as possible. Additionally, the usual routine of families especially ones with young children was discussed to identify mutually convenient times during the day when shoots could be organized to capture specific interactions. For play activities, existing reference videos and suitable coaching was also given to caregivers. Specific planning was done to include families and caregivers of both male and female children, belonging to varied social and religious groups to ensure equitable representation.

Content and structure of *Aalana Palana* videos: The videos promote responsive and sensitive parenting, early learning opportunities and desired nutritional practices for young children and pregnant women. The content not only describes 'WHAT' behaviours caregiver should adopt, 'HOW' they could include these behaviours in their routines but also 'WHY' a particular behaviour is important for their child's development.

Each 5–6-minute video is divided into three segments which focus on a specific set of parenting practices. At the end of each segment instructions are displayed to pause and discuss key issues on the viewed content. These pauses are aimed at facilitating a two-way communication between AWWs and their audience, while providing listeners an opportunity to share their opinions and concerns regarding the topics being discussed. At the end of each video, a *sutradhaar* (narrator), who is a well-known media personality from Telangana (23), summarizes key takeaways and actionable practices. To address specific behaviours, shorter 1–2-minute variants of these videos were developed and shared with caregivers which were derived from the 5–6-minute videos.

Feedback on video content: During the production and post-production phases of the video content development, stakeholders from DWDCW, UNICEF and the Sangath team iteratively provided feedback to the creative team. These recommendations on organization of visuals in each video, language used in scripts, voice modulation, and cultural diversity of content were used to refine the videos.

Implementation of Aalana Palana

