For the purposes of this study, exposure will be defined as having watched any *Aalana Palana* video within the three-month period preceding data collection.

Outcome Measures

Child development outcomes will be measured using three validated tools appropriate for low- and middle-income country (LMIC) settings:

1. **Family Care Indicators (FCI)** (26)– Developed by UNICEF and adapted from the HOME inventory, this caregiver-report tool assesses the quality of the home environment, focusing on caregiving practices that support early child development in children aged 0–5 years. The FCI includes yes/no items covering the availability of and variety in play materials and play-related activities.

2. **Infant and Young Child Feeding (IYCF) Framework** (27)– This tool captures data on key nutrition indicators, particularly breastfeeding and complementary feeding practices for children under two years of age. It follows WHO and UNICEF recommendations and includes 17 operationally defined indicators to assess adequacy in early feeding practices.
3. **Caregiver Reported Early Development Instruments (CREDI)** (28)– Designed to measure developmental progress in children aged 0–36 months, this population-level, caregiver-reported tool assesses four domains: motor, language, cognitive, and socio-emotional development. The long-form, which includes 108 items, will be used. With necessary permissions, the CREDI tool has been translated into Telugu by the Sangath team to ensure cultural and linguistic relevance for the study population.

These tools have been selected for their strong psychometric properties, appropriateness for use in community settings, and feasibility for administration by trained data collectors.

Data collection

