Two different teams were deployed to collect data between July 2023 and January 2024. This was done to minimize assessor bias by ensuring that exposure and outcome data was collected by two separate teams. The first team comprised of two field workers who mapped the study geography, consented eligible participants, and collected data on geolocations, demographic, socio-economic, and exposure to *Aalana Palana*. The list of consented participants identified by the first team was shared with a second team who visited the households three-to-four weeks post consenting. The second team of non-specialist child development assessors collected all outcome data on FCI, CREDI, and IYCF practices. Data on IYCF practices was collected from a subset of children aged >6 months and <2 years at the time of data collection.

Data Analysis

All data will be analyzed using Stata 15 and SPSS 27.

- Descriptive Analysis: Frequencies, means, and standard deviations will be used to summarize participant characteristics, exposure levels, and outcomes. Group differences will be tested using chi-square tests for categorical variables and t-tests for continuous variables.
- Primary Analysis: Linear regression will be used to estimate the association between intervention exposure and CREDI z-scores, adjusting for child age, child sex, maternal education, FCI score, and AWC registration status.
- Secondary Analyses:
 - Logistic regression will assess the association between exposure and binary outcomes for FCI and MAD.
 - Moderation analysis will examine interaction effects of child age, sex, and maternal education on the primary outcome.

- Mediation analysis will be conducted using structural equation modeling (SEM) to assess whether the effect of the intervention on child development is mediated by the quality of the home environment (FCI score).

Sensitivity Analysis: Subgroup analyses will be performed for caregivers registered at AWCs to account for potential confounding due to engagement with AWC services.

Data Management and Confidentiality

Data will be collected digitally on secure tablets using encrypted platforms (e.g., REDCap). Data will be uploaded to a password-protected server accessible only to designated research personnel. Identifiers will be stored separately from de-identified datasets. Regular backups and integrity checks will ensure data security and accuracy.

Ethics Approval and Consent

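### The primary CREDI regression adjusts for FCI score, which the plan also treats as an outcome and as the mediator, so it does not estimate the programme's total effect

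*Combined protocol and SAP*

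**What the plan says.** Under Data Analysis, the primary analysis is a linear regression on exposure of "CREDI z-scores, adjusting for child age, child sex, maternal education, FCI score, and AWC registration status".

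The same section uses FCI in two other ways:

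- As an outcome: "Logistic regression will assess the association between exposure and binary outcomes for FCI and MAD".
- As a mediator, in a structural equation model meant to "assess whether the effect of the intervention on child development is mediated by the quality of the home environment (FCI score".

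Under Data collection, the first team records exposure at consent. The second team visits three to four weeks later: "The second team of non-specialist child development assessors collected all outcome data on FCI, CREDI, and IYCF practices". The Limitations section states that there are no baseline data.

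On content, the intervention section says: "The videos promote responsive and sensitive parenting, early learning opportunities and desired nutritional practices for young children and pregnant women". Under Outcome Measures: "The FCI includes yes/no items covering the availability of and variety in play materials and play-related activities". The introduction gives the aim as effectiveness for child development and for the home caregiving environment, and Study Design and Participants speaks of impact.

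One other planned analysis may compare CREDI between groups without FCI, in the descriptive section: "Group differences will be tested using chi-square tests for categorical variables and t-tests for continuous variables".

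**The concern.** A covariate used to control confounding should not itself be a consequence of the exposure. Here FCI is measured after exposure, covers behaviour that the videos set out to change, and is the plan's own candidate for the causal pathway. Conditioning on it has two effects:

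- It takes out of the exposure coefficient whatever part of the effect runs through measured FCI.
- If unmeasured factors drive both FCI and CREDI, it opens a collider path and adds bias.

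The more the programme works as its designers expect, by improving the home environment, the smaller its primary estimate becomes. A small result could then be misread as an ineffective programme. Nothing in the plan labels the coefficient a direct effect or justifies conditioning on FCI.

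The other planned analyses are only partial substitutes. The t-tests have no adjustment, although Limitations relies on multivariable regression against confounding. The SEM separates an indirect path, but the plan does not commit to reporting a total effect. The AWC-registered subgroup analysis restricts the sample, and nothing says that it drops FCI.

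**Working it through.** The plan gives no figure to reproduce: no effect size, SD, sample size or power. Every value below is an assumption, in SD units, with half the sample exposed.

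**Model.** Exposure X. Prior home environment P, differing by δ between groups. A common cause U of FCI and CREDI, independent of X.

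- FCI: M = aX + rP + gU + error, SD 1 within group.
- CREDI: Y = c′X + bM + qP + dU + error, SD 1 within group.
- Total effect T = c′ + ab. With mediated share s, b = sT/a and c′ = T(1 − s).

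The group difference in FCI is D = a + rδ. The exposure coefficients are:

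- without FCI: c′ + bD + qδ
- with FCI: (c′ + bD + qδ) − (b + rq + gd)D

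**1. Mediation only** (T = 0.20, a = 0.30, r = q = g = d = δ = 0). The coefficient without FCI is 0.20; with FCI it is c′.

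Let R² be the share of FCI variance explained by exposure: 0.25 × 0.30² / (1 + 0.25 × 0.30²) = 0.0225/1.0225 = 0.022. The ratio of standard errors, without FCI to with FCI, is k = √[(1 − R²)/(1 − b²)]. A sample with 80% power for T has noncentrality 1.96 + 0.84 = 2.80, so the FCI-adjusted test has 2.80 × (1 − s) × k (two-sided 5%).

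| s | b | Coefficient with FCI | k | Noncentrality | Power |
|---|---|---|---|---|---|
| 25% | 0.167 | 0.15 | 1.003 | 2.11 | 56% |
| 50% | 0.333 | 0.10 | 1.049 | 1.47 | 31% |
| 75% | 0.500 | 0.05 | 1.142 | 0.80 | 13% |

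The last row needs a strong FCI–CREDI slope (0.5).

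**2. One gap between models, several explanations.** A difference of about 0.03 SD can arise from:

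- 15% mediation: 0.20 without FCI, 0.20 × 0.85 = 0.17 with it.
- No mediation, but a common cause with g = d = 0.3: 0.20, then 0.20 − 0.09 × 0.30 = 0.173.
- No effect at all (T = a = 0), with δ = 0.4, r = 0.5, q = 0.3: 0.3 × 0.4 = 0.12, then 0.12 − 0.15 × 0.20 = 0.09.

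**3. Which model lies closer to T?** Take T = 0.20, a = 0.30, s = 50%, r = 0.5, q = 0.3, with no U.

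- Bias without FCI: (0.333 × 0.5 + 0.3)δ = 0.467δ.
- Bias with FCI: −0.483 × 0.30 + (0.467 − 0.483 × 0.5)δ = −0.145 + 0.225δ.
- Absolute biases are equal at δ = 0.145/(0.467 + 0.225) = 0.21 SD.

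Below 0.21 the model without FCI is closer; above it the FCI-adjusted model is. I then varied T (0.1, 0.2, 0.3), a (0.2, 0.3, 0.5), s (10, 25, 50, 75%), r (0.3, 0.5, 0.7) and q (0.2, 0.3, 0.5). Of 324 sets, 18 have non-positive residual variance; in the other 306 the crossover runs from 0.04 to 0.49 SD.

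**4. The t-test as substitute.** An imbalance in maternal education of 0.2 to 0.4 SD, with a slope of 0.2 to 0.3 on CREDI, shifts an unadjusted contrast by 0.2 × 0.2 = 0.04 to 0.4 × 0.3 = 0.12 SD.

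**5. Measurement error.** FCI is caregiver-reported. In a simulation with a = b = 0.3 and c′ = 0.1 (total 0.19), adjusting for error-free FCI gives 0.10; at reliability 0.7 it gives 0.13. Error therefore leaves part of the mediated path in the coefficient.

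**The case against.** The best defence is confounding. Viewing is self-selected and the comparison group is a convenience sample, so homes that watched may already have been more stimulating. FCI is the only home-environment variable in the model, and dropping it may leave upward bias. In the grid above, the crossover falls below 0.20 SD in 60% of sets and below 0.30 SD in 88%. At a prior difference of 0.30 SD the plan's model would thus be closer to the total effect in most sets. These are counts over a chosen grid without collider terms, not probabilities.

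This stands as a reason to keep the FCI-adjusted model on view. It does not rescue that model as the primary one. The plan never makes the argument, and an FCI taken after exposure cannot separate the prior home from the programme's effect.

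Three further points are fair:

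- FCI may also reflect earlier viewing, since sessions began in January 2022 and exposure counts only the last three months. It is then not purely a mediator of exposure as defined.
- The plan words the primary result as an association, and the SEM's direct and indirect paths could be added up. But the SEM is secondary and no total effect is promised.
- The first team collected socio-economic data, a partial pre-exposure proxy that the primary model does not use.

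These refine the point; the inconsistency remains.

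**Conclusion.** The concern holds. Without confounding or measurement error, and with no exposure-by-FCI interaction, the primary coefficient falls short of the total effect by exactly the mediated share: 0.05, 0.10 or 0.15 SD out of an assumed 0.20 SD at 25, 50 or 75% mediated. Measurement error in FCI makes the loss smaller; common causes of FCI and CREDI that act in the same direction on both make it larger. Confounding by the prior home works the other way.

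Confidence is high that the primary model does not match the study's question and that the plan does not say which effect it estimates. The direction and size of the net bias cannot be settled from the documents. The power figures describe the assumed scenario, not this study.

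**What to change.** - State that the primary model targets the total effect of exposure. Remove FCI score from its covariates, leaving child age, child sex, maternal education and AWC registration status. Consider adding the socio-economic data already collected.
- Report the FCI-adjusted model beside it as a direct-effect or sensitivity estimate. Add the caveat that the two may differ through mediation, collider bias or confounding by the prior home.
- Keep FCI as a secondary outcome and as the SEM mediator, and commit to reporting direct, indirect and total effects.
- Date the change, disclose that it came after data collection, say whether CREDI had already been compared by exposure, and show both models whatever they give.

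The cost is a few sentences and one more regression on data already held. There are three downsides:

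- **Precision.** Under scenario 1 the exposure standard error without FCI is about 0, 5 or 14% larger at 25, 50 or 75% mediated. If the effect on FCI is varied from 0.5 to 0.2 SD, the range is 2% smaller to 50% larger; the upper end needs a slope of 0.75.
- **Residual confounding** by the prior home. Two models make it visible but do not remove it.
- **Timing.** On the dates, "Two different teams were deployed to collect data between July 2023 and January 2024", and the document is dated 14 May 2025. A change now could look result-driven unless it is disclosed as above.

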Given these challenges, the study will build on existing collaborations between Sangath, UNICEF, and the Department of Women Development and Child Welfare (DWDCW), Government of Telangana. The intervention, *Aalana Palana*, is proposed to be implemented within the Integrated Child Development Services (ICDS) framework (15). This initiative would be delivered across 30 Anganwadi Centres (AWCs) spanning three ICDS projects: Maheshwaram, Khairtabad, and Alwal. AWCs serve as key community-level service delivery points, catering to approximately 5,000 people in urban and 1,000 in rural areas, and are managed by Anganwadi Workers (AWWs), a cadre of community-based frontline workers.

A key enabling factor for intervention delivery in this context is the widespread mobile phone access in Telangana, with 96% of urban and 91% of rural households owning a mobile phone. Furthermore, 60% of women in the state have access to a mobile phone that they use personally, which enhances the feasibility of integrating digital or hybrid models of ECD delivery (14).

This context provides a strong foundation to evaluate and scale integrated, community-based, and technology-supported ECD interventions within public systems like the ICDS in Telangana.

The Aalana Palana Intervention

Aalana Palana is a facilitated video-viewing intervention combining responsive parenting and nutrition messaging. *Aalana Palana* which, in the local language Telugu, translates to ‘caring and nurturing’, represents a transition from largely paper-based counselling sessions to a facilitated video viewing, discussion and demonstration model. It aims to ensure fidelity of the intervention delivery by standardising the content delivered during sessions. AWWs would use these videos to conduct both individual and group counselling sessions with caregivers at AWCs and family homes. *Aalana Palana* was developed using the following steps:

Development of video content

Information synthesis: A desk review of published global research on parenting interventions specifically in LMICs, the Nurturing Care Framework (16), the WHO Care for Development Package (17), and the early years learning framework. Resources in the Indian context, such as the Mother and Child Protection card (18), Home-Based Care for Young Child (HBYC) program guidelines, Poshan Abhiyan (19), and *Intintiki Anganwadi* (20), were also reviewed for content and implementation guidelines.

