Training plan: Consultations with DWDCW and UNICEF were conducted to develop a capacity building plan which would be integrated within the existing training schedules of AWWs. A three-day training of four hours was implemented that focused on experiential

learning and role plays. Training content included session plans, learning objectives for each session, and expected competencies required for the delivery of *Aalana Palana*. The topics covered - importance of the early years of life and responsive caregiving, objectives of *Aalana Palana*, intervention content, values of two-way communication, intervention delivery processes, and supportive supervision. *Aalana Palana* videos were also uploaded on the phones of the AWWs using external solid-state drives and they were trained to select age-specific videos for session delivery.

In December 2021, 30 AWWs from three ICDS projects, along with their supervisors and Child Development Project Officers (CDPOs), underwent in-person training. Pre and post-tests were done at the beginning and end of each training day to understand any changes in knowledge and obtain feedback about sessions from AWWs.

Session delivery: Qualitative research conducted during the formative stage of *Aalana Palana* highlighted challenges on time use and workload of AWWs (21). One of the mitigation strategies that emerged during further consultations with AWWs which could facilitate effective implementation of *Aalana Palana* was the prioritisation of group over individual counselling sessions. Evidence also indicated benefits of parenting interventions involving group-based sessions on child outcomes, particularly in LMICs (24). Based on this, AWWs were encouraged to use the *Aalana Palana* videos primarily during group-based counselling sessions. AWWs started delivering *Aalana Palana* sessions from January, 2022.

Supportive supervision: The *Aalana Palana* team conducted at least one in-person supervision visit per month for all 30 AWWs and used a semi-structured questionnaire to observe the sessions. To record session delivery, stickers were placed next to the names of caregivers in existing registers maintained by AWWs.

The process of *Aalana Palana* video development and implementation can be seen in Figure 1.

[figure not shown]

Figure 1: Process of Aalana Palana video development and implementation

Study Design and Participants

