To assess the impact of the *Aalana Palana* intervention, we propose a quasi-experimental, non-randomized post-test only design incorporating a convenience-based comparison group. The study will be conducted in the catchment areas of 30 Anganwadi Centres (AWCs), previously identified as implementation sites through partnerships with government and community stakeholders.

Household mapping within these catchment areas will be undertaken to identify eligible participants, specifically caregivers of children under three years of age. All eligible participants who provide informed consent will be included in the study. The intervention (or “exposed”) group will comprise caregivers who report having viewed an *Aalana Palana* video within the three months preceding data collection.

A comparison (unexposed) group will be formed using a convenience sampling approach, including participants from the same catchment areas who have not been exposed to the intervention. Importantly, participation in the study will not be restricted to households registered at an AWC, allowing for the inclusion of a broader range of community members and enhancing the generalizability of findings within the selected geographies.

This design enables the assessment of real-world exposure and its potential effects under naturalistic conditions while acknowledging limitations related to non-random allocation.

Data Collection Tools

For all participants who consent to participate in the proposed study, basic demographic and identifying information will be collected, including GPS coordinates of households; child’s name, sex, and date of birth; names and dates of birth of parents; contact details; address; and maternal education level. Maternal education will be categorized using classifications from the modified Kuppuswamy scale (25), which has been adapted for Indian socio-economic contexts.

Assessment of Exposure to Aalana Palana

Exposure to the *Aalana Palana* intervention will be determined through a structured set of questions developed by the intervention team. These will include:

- (i) Whether the participant has heard of *Aalana Palana* (with follow-up on the source of information);
- (ii) Whether the participant has watched any *Aalana Palana* video in the three months prior to data collection;
- (iii) Whether anyone in the household has any *Aalana Palana* video stored on their mobile device (with follow-up on the source).

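### The primary model has no term for Anganwadi Centre or ICDS project, so differences between centres may bias the exposure coefficient, by an amount and in a direction the documents do not allow us to work out

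*Combined protocol and SAP*

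**What the plan says.** Under Data Analysis, the Primary Analysis bullet states: "Linear regression will be used to estimate the association between intervention exposure and CREDI z-scores". The covariates follow in the same sentence, which describes the model as "adjusting for child age, child sex, maternal education, FCI score, and AWC registration status". That is the whole covariate list. The logistic models for FCI and MAD, the moderation analysis and the mediation analysis name no site term either. The one sensitivity analysis restricts to caregivers registered at an AWC and still pools all centres. The Limitations section acknowledges confounding and selection bias but does not mention site.

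The relevant design facts are these:

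- Study Setting: the intervention is delivered in "30 Anganwadi Centres (AWCs) spanning three ICDS projects: Maheshwaram, Khairtabad, and Alwal". The same section describes AWCs in general as "catering to approximately 5,000 people in urban and 1,000 in rural areas". It does not say which study centres are urban or rural.
- Training plan: "30 AWWs from three ICDS projects, along with their supervisors and Child Development Project Officers (CDPOs), underwent in-person training". Thirty workers for 30 centres suggests one worker per centre, in which case centre and worker cannot be separated.
- Assessment of Exposure: "exposure will be defined as having watched any" Aalana Palana video during the preceding three months. Exposure is an individual self-report and is not allocated by site.
- Study Design and Participants: the comparison group is a convenience sample, "including participants from the same catchment areas who have not been exposed to the intervention". No quota, matching or balancing within a centre is described.
- Data Collection Tools: household data are collected "including GPS coordinates of households".

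**The concern.** Both groups come from the same 30 catchments, so the data could support a comparison within each centre. The planned model does not make that comparison. Its coefficient mixes within-centre contrasts with differences between centres.

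A caregiver's chance of having watched a video depends on how much the local worker delivers, and plausibly on how many families that worker has to cover. Child development may also differ by centre, for example through setting or household circumstances that maternal education does not capture. Where exposure and outcome vary together across centres, that difference enters the exposure coefficient. Registration status records whether a family is registered, not at which centre, in which setting or with which worker.

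This concerns the estimate and not only its standard error: cluster-robust errors would leave the coefficient unchanged. At stake is whether a reader can tell an association that arises within centres from one that reflects which centres delivered more.

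**Working it through.** The plan gives no sample size, effect size, exposure rate, site-level outcome or intracluster correlation. There is no figure to reproduce, and everything below is illustrative.

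**Formula.** Bias ≈ d × (rural share among exposed − rural share among unexposed), where d is the rural-minus-urban CREDI difference, in SD, that remains after the listed covariates.

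**Inputs from the documents.** 30 centres; about 5,000 people per urban and 1,000 per rural AWC.

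**Base-case assumptions, not in the documents.** 10 rural and 20 urban centres; 5% of people under three (50 children per rural centre, 250 per urban); 20 caregivers reached per worker in either setting; every eligible household enrolled; d = −0.1 to −0.3.

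**Base case.**

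- Exposure rate: rural 20/50 = 40%, urban 20/250 = 8%.
- Exposed: 10×20 = 200 rural and 20×20 = 400 urban; rural share 200/600 = 0.333.
- Unexposed: 10×30 = 300 rural and 20×230 = 4,600 urban; rural share 300/4,900 = 0.061.
- Difference 0.272; bias −0.027 (d = −0.1) to −0.082 (d = −0.3).

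**Varying the assumptions.**

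| Scenario | Rural share, exposed | Rural share, unexposed | Difference | Bias, d = −0.1 to −0.3 |
|---|---|---|---|---|
| 5 rural centres, reach 10 | 0.17 | 0.03 | 0.13 | −0.013 to −0.040 |
| 20 rural centres, reach 30 | 0.67 | 0.15 | 0.51 | −0.051 to −0.154 |
| Base case, urban reach 40 | 0.200 | 0.067 | 0.133 | −0.013 to −0.040 |
| Base case, urban reach 100 (equal rates) | 0.091 | 0.091 | 0 | 0 |
| Base case, same number of unexposed enrolled per centre | 0.333 | 0.333 | 0 | 0 |
| All centres of one type | – | – | 0 | 0 |

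The bias is also zero if d = 0, and it changes sign with d.

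**Does an AWC term remove it?** A simulation of the base case used 400 runs, a true effect of 0.20 SD and centre exposure rates varying around the values above. It compared ordinary regression without and with AWC indicators, with no other covariates. Mean estimates were:

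- d = −0.2: 0.148 without, 0.203 with.
- d = +0.2: 0.254 without, 0.199 with.
- d = −0.3, centre SD 0.15: 0.115 without, 0.197 with.
- No urban-rural gap, centre SD 0.15, correlation 0.5 between a worker's delivery and the centre's outcomes: 0.224 without, 0.200 with.
- Equal exposure rates in both settings, d = −0.2, centre SD 0.15: 0.200 without, 0.200 with.

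Empirical standard errors across all scenarios were 0.038 to 0.049 without AWC terms and 0.035 to 0.048 with them.

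**Why the loss of precision is small.** It depends on the share of exposure variance that lies between centres. In the base case, overall exposure is 600/5,500 = 0.109, with variance 0.109×0.891 = 0.097. The between-setting part is (500/5,500)×(5,000/5,500)×(0.40−0.08)² = 0.0085, about 9% of the total. The standard error therefore rises by a factor of about 1/√0.91 = 1.05 when centres differ in nothing but setting. The 5,500 children are a consequence of the assumptions and not a planned sample size.

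**The case against.** The strongest reply is that omitting site does not establish bias. A reader might infer that the 5,000 and 1,000 catchment figures imply very different exposure rates in this study, and so a bias of known order. Stacking 20 rural centres, 3% under three, 25 caregivers reached per worker and a 0.3 SD gap gives a share difference of 0.59 and a bias of 0.59×0.3 = 0.18 SD. The documents do not support that reading:

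- The catchment figures describe AWCs in general, and no study centre is labelled urban or rural.
- Equal reach per worker has no source. Workers were encouraged to use group sessions, short versions of the videos were shared with caregivers, and videos may be stored on household phones, so reach need not be tied to a worker's one-to-one time.
- The calculation needs full enrolment. Study Design and Participants says that all consenting eligible caregivers are included, but also that the comparison group is a convenience sample. With equal reach and similar unexposed numbers per centre, the bias vanishes.
- Maternal education, FCI score and registration status may absorb part of any gap between sites.
- All 30 workers had the same training and at least monthly supervision. That more active workers also achieve better outcomes by other routes is conjecture.

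All of this stands against any claim of a known bias. It does not show that site is balanced. Session delivery records workload as a constraint on workers, so reach cannot be presumed to grow in proportion to the catchment. In the base case, even urban reach double the rural leaves a share difference of 0.13.

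Two further objections carry less weight. The plan speaks of an association and admits non-random allocation, but a general caveat does not replace an adjustment the data can probably support. Data collection ended in January 2024 and the document is dated May 2025, so the primary model would change after collection. The analysis is nevertheless still written in the future tense.

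**Conclusion.** The point holds as a possible bias of unknown size and sign. It rests on three facts in the documents: no analysis contains a site term, exposure is delivered through each centre's worker, and exposed and unexposed caregivers are not balanced within centre. Bias arises only if exposure among those enrolled and outcomes left after covariates both differ by centre. Different worker activity or catchment size makes that plausible, but the documents quantify neither.

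The illustrative scenarios run from zero to about 0.15 SD in absolute size, with −0.03 to −0.08 SD in the base case. The worker-related scenario moved the estimate by only about 0.02 SD. None of these is an estimate for this study.

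A reader might also infer that the missing site term is what prevents the result from being read as an effect of viewing. That goes too far: self-selection into viewing within a centre already stands in the way, and AWC terms would not remove it.

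**What to change.** - Add AWC indicator terms to the primary CREDI model, so that exposed and unexposed caregivers are compared within the same AWC.
- Use AWC indicators in the FCI and MAD logistic models too, falling back on ICDS project indicators where centres are too sparse, with the sparseness rule set before fitting. The fallback is most likely to be needed for MAD, because feeding data come only from children older than 6 months and younger than 2 years.
- Report exposure prevalence by AWC and by project in the descriptive table. This shows directly whether exposure varies enough between centres for the concern to matter.
- Because data collection is complete, record the change with its date and reason, and show the planned five-covariate model alongside.

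The cost is up to 29 degrees of freedom, and centres with only exposed or only unexposed caregivers no longer inform the coefficient. No new data collection appears necessary. AWC is not listed as a recorded variable, but the catchment mapping, household GPS and addresses should allow each household to be assigned to a centre; that feasibility is inferred and should be confirmed.
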